8.2.5. Organization of data collection

- The students who are employed for the recruitment of participants and the data collection are trained by the researcher.
- There is a budget calculated (see Annex 2). Each interview of one patient will last on average one hour, considering that all questionnaires together have 273 items. You could do two interviews in half a day, but you need a lot of preparation and aftercare for each visit.

8.4 Participating sites

The following IMR-teams (teams for outpatient care)/ locations within BavoEuropoort will participate in the study:

IMR Team Noord Oudedijk (Rotterdam)

IMR Team, Oost Oudedijk (Rotterdam)

Time-out Team Carnissesingel (Rotterdam)

IMR Team Zuid Carnissesingel (Rotterdam)

IMR Team Centrum Westblaak (Rotterdam)

IMR Team Zuid-Hollandse Eilanden (Spijkenisse).

9 Statistics

- For measurement of the effects of the IMR-training on the primary outcome measure, and on secondary outcomes on three moments of measurement we use Linear Mixed Models.

Differences in time between groups can be examined with cross level interaction for time x group interaction effect.

- The groups are compared at the final and follow-up assessments in terms of a main group effect, to test the question whether the groups differ after treatment, controlling for baseline.
- For validation of the scores on the primary outcome measure on different aspects of Illness Management (Stress, Social Support, Medication adherence, Drugs use, Symptoms/Remission/Relapse, Coping) we use multiple regression analysis, logistic regression analysis and multinomial analysis.

'For prediction of the effect on the primary outcome measure using the baseline data in terms of functioning (scores on IMR-scales, GAF-scores, Social Functioning Scale and BSI) we use linear regression analysis.

For prediction of the effect on the primary outcome measure using the baseline data in terms of patient characteristics (gender, etnicity, diagnosis) we use t-tests and one way ANOVA.'

If we find effects of the IMR-training on the Distal outcome measures of recovery:
 to determine the influence of Illness management aspects as mediating factors on the effects on recovery we use Multiple Mediator Analysis for SPSS (Preacher & Hayes, 2008).

10 Feasibility of the study

The organization of the IMR training and the organization and logistics of the research require a major effort by Bavo Europoort and the research team.

Given the successful progress of the pilot study it seems that the RCT-study is quite feasible. IMR has become a familiar type of care in the outpatient teams and there is enthusiasm among clinicians and patients. Moreover, there is now an infrastructure for training and supervision of the IMR trainers. Data collection in the pilot study went relatively smoothly. It is difficult to predict the effect of the randomization procedure on the willingness of the patients to participate in the study.

A patient who accepts participation in the control group is essentially ineligible for IMR for a period of 1.5 years. Earlier research showed that about 50% of patients are willing to participate in such an investigation (Henderson et al 2004). Participation often appears very dependent on how clinicians and researchers approach the patient.

For the 85 patients who supposedly will be in an IMR-group in the experimental condition 10 IMR groups need to start in the first year of data collection (baseline measurement). This requires 20 trainers.

The 6 IMR-teams of Bavo Europoort have approximately 60 employees. Everyone is trained in IMR. It is therefore theoretically feasible to undertake the study, and would also make IMR a more explicit component of the care provisions of the group. However, to implement IMR on such a broad scale and to participate in the study is still a challenge for the institution.

We fully anticipate that the enthusiasm of clinicians for this study will lead to the inclusion of the required patient numbers for the study.

11 Time frame

The planning is based on a period of 1 year in which 14 IMR-groups will start and the baseline measurements of all patients will be obtained.

The duration of the 6-IMR groups in the pilot was on average 12.6 months. The following schedule has been assumed that the duration of the groups is 12 months.

Start: April 1th 2011

0 - 15 months (July 2012). Writing definitive protocol, asking permission of medical ethical committee, request of additional grant, training in IMR fidelity-scale, informing clinicians, management, recruitment of students.

15 months (July 2012)- 29 months (September 2013)., training of students, patient recruitment, baseline measurements

17 months (Sept 2012) - 41 months (September 2014). IMR program is offered.

29 months (Sept 2013) - 41 months (September 2014) Second measurements

35 months (February 2014) - 47 months (March 2015). Follow-up measurements

47 months (February 2015) - 60 months (June 2016). Entering data into the computer, analysis and reporting of results. Processing of data in articles and a dissertation

The expected completion date of the study is July 1th, 2016.

12 Ethical considerations

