The implementation of IMR at BavoEuropoort has been evaluated with a pilot study, which aims to provide guidelines for an optimal implementation of IMR. This pilot study was also intended as a preparation for the RCT. The report of the pilot will be completed during the course of 2012. Some results are:

- Completers seem to benefit from IMR.
 More women complete IMR
- Completers at baseline score significantly better than non-completers on the IMR-scale client version, IMR-scale clinicians version and on the GAF (psychosocial functioning)
- The fidelity of implementation varies by group and appears to be related to the quality of the trainers.
- The supervision of the trainers needs a substantial boost.
- There is a high rate of drop-out from treatment, especially in the stages prior to the start of the IMR Group.
- The participants who at the start score better on the IMR-scales have a relatively lower drop-out.
- Recruitment of participants in IMR is not easy.
- Given the successful progress of the pilot study it seems that the RCT-study is quite feasible. Data collection in the pilot study went relatively smoothly.

Status of IMR as an Evidence-Based Practice (EBP)

The IMR program was developed in the United States as part of the National Implementing Evidence-Based Practices Project, a major project to implement six evidence-based care programs in the U.S (Drake et al., 2001; Mueser et al., 2003). Other EBP-programs in this project are Assertive Community Treatment (ACT), Integrated Dual Disorder Treatment (IDDT), Individual Placement and Support (IPS), Family Psycho Education (FPE) and Medication Management (MM). With evidence-based we mean that research has given conclusive support that the treatment type is effective.

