5.3 Sample Size

Based on the effect sizes of the studies of Hasson et al. (2007) with 210 participants (.41, Cohen's d), Levitt et al. (2009) with 104 participants (.36) and Färdig et al. (2011) with 41 participants (.60) we expect a medium effect size of 0.40.

Based on the power analyses with three moments of measurement (mixed models) and equal allocation to experimental and control group, a power of .80, correlation between measures .50, alpha at 0.05 and an effect size of .40, we need to randomize 148 patients, 74 to the experimental condition and 74 to the CAU-group (see Twisk (2003) and Guanghan L. and Kung-Yee L. (1997).

Because of the (conservatively estimated) expected drop-out from treatment in the experimental condition of 50% we choose to allocate more patients to the experimental (IMR-) condition than to the CAU-group (proportions of 3:2). Then we need to randomize 185 patients, 111 patients to the experimental condition and 74 to the CAU-group.

Because we expect a total drop-out in each group from measurements of 8 % we need 80 patients in the control condition and 120 patients in the experimental condition. In total: 200 patients (see Annex 1).

6. Intervention

The average duration of the total IMR-training is 12 months. The IMR-training consists of 11 modules that are given weekly. The first module is given individually. During this individual module the patients decide which goals they want to work on during the program.

Then the patients join an IMR group for the other modules. Each module takes about 3 to 4 sessions of one and a half hours each. The IMR group is guided by two trainers (psychiatric nurses). The trainers received a two-day course in IMR and attend supervision once every two weeks.

The modules are described in the IMR-workbooks, translated into Dutch, which the patients received. If necessary, the original American text is adapted to the Dutch context. The modules are: 1. Recovery Strategies, 2. Practical Facts about Mental Illness, 3. Stress-Vulnerability Model, 4. Building Social Support, 5. Using Medication Effectively, 6. Alcohol and Drugs Use, 7. Reducing Relapses, 8. Coping with Stress, 9. Coping with Problems and Persistent Symptoms, 10. Getting Your Needs Met in the Mental Health System, 11. Health for you.

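### Section 5.3 sizes the trial as if all patients were independent, with no allowance for IMR being given in trainer-led groups in one arm only

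*Protocol*

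**What the plan says.** **Sample size (section 5.3).** Under mixed models with three measurement moments, the inputs are "equal allocation to experimental and control group, a power of .80, correlation between measures .50, alpha at 0.05 and an effect size of .40". The result is "we need to randomize 148 patients, 74 to the experimental condition and 74 to the CAU-group". The IMR arm is then enlarged to 111 (3:2), and the only reason given is an expected 50% drop-out from treatment. An 8% loss to measurement brings the total to 120 + 80.

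**Delivery (sections 6 and 7).** Module 1 is individual. "Then the patients join an IMR group for the other modules", with two trainers per group and an average course of 12 months. Control patients see a community psychiatric nurse individually.

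**Pilot (section 1.1).** "The fidelity of implementation varies by group and appears to be related to the quality of the trainers".

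**Analysis (section 9).** For the primary outcome and "on secondary outcomes on three moments of measurement we use Linear Mixed Models", with a time-by-group term, where group means trial arm. No random effects are listed.

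**Number and size of groups.** Section 8.2.1 expects about 78 patients to start the groups. Section 10 says: "For the 85 patients who supposedly will be in an IMR-group in the experimental condition 10 IMR groups need to start". Section 11 says: "The planning is based on a period of 1 year in which 14 IMR-groups will start".

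**The concern.** Patients who spend about a year in the same group, with the same two trainers and with peer support as part of the training, may have correlated outcomes. Because this happens in one arm only, the design is partially nested. Any positive ICC increases the variance of the IMR arm mean, so a sample size for independent patients gives less power than stated. If the analysis also left out the group level, the standard error of the arm contrast would be too small and the test too liberal. The pilot finding makes a group effect plausible, yet nothing in section 5.3 reflects it. Group size, which any allowance needs, cannot be read off because the protocol's own counts conflict.

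**Working it through.** **Inputs from the protocol.** d = 0.40, alpha 0.05 (sidedness not stated; two-sided assumed), power 0.80, correlation 0.50 (section 5.3). Share of the IMR arm that starts a group: 78/120 = 0.65 (section 8.2.1). Patients per group from sections 8.2.1, 10 and 11: 78/14 = 5.6, 85/14 = 6.1, 78/10 = 7.8, 85/10 = 8.5. I use m = 6 to 8.5.

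**Assumed.** ICC of 0.01, 0.05 and 0.10, applied to the analysed outcome.

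**Step 1: reproduce 74 per arm.** For T averaged measures on independent patients, n per arm = 2(1.960 + 0.842)² × [1 + (T−1)ρ]/T ÷ d².
- T = 2 (the two post-baseline measures): factor (1 + 0.5)/2 = 0.75, so n = 73.6, or 74, with power 0.802. Baseline-adjusted analysis of one follow-up gives the same factor, 1 − 0.5² = 0.75.
- T = 3: factor 0.667, n = 65.4, or 66. This does not match.
- One unadjusted measure: n = 98.1, or 99. This does not match.

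So 74 is the independent-patient figure with variance factor 0.75.

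**Step 2: add clustering in the IMR arm only.** DE = 1 + s(m − 1)ICC, with s = 1 (all IMR patients clustered) or s = 0.65 (group starters only). SE = √[0.75 × (DE/n_IMR + 1/n_CAU)]. Power = Φ(0.40/SE − 1.96).

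Example with m = 8.5, ICC 0.05, s = 1, 74 + 74: DE = 1.375; SE = √(0.75 × 2.375/74) = 0.155; power = Φ(2.58 − 1.96) = 0.73.

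| Assumed ICC | Power at 74 + 74, s = 0.65 | Power at 74 + 74, s = 1 | Per arm needed for 80% at 1:1 |
|---|---|---|---|
| 0 | 0.80 | 0.80 | 74 |
| 0.01 | 0.79-0.80 | 0.79 | 75-77 |
| 0.05 | 0.76-0.77 | 0.73-0.76 | 80-88 |
| 0.10 | 0.71-0.74 | 0.67-0.71 | 86-102 |

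**Step 3: the planned 111 versus 74, at the full d = 0.40.** If the model ignores IMR group, the true two-sided type I error is 2Φ(−1.96 × SE₀/SE), where SE₀ is the value at DE = 1.

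| Assumed ICC | Power, s = 0.65 | Type I error if group ignored, s = 0.65 | Power, s = 1 |
|---|---|---|---|
| 0 | 0.87 | 0.050 | 0.87 |
| 0.01 | 0.86 | 0.051-0.052 | 0.86 |
| 0.05 | 0.84-0.85 | 0.058-0.061 | 0.82-0.84 |
| 0.10 | 0.80-0.83 | 0.065-0.073 | 0.77-0.80 |

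**Step 4: where power at 111 versus 74 reaches 0.80.** Solve 0.75 × (DE/111 + 1/74) = (0.40/2.80)², which gives DE = 1.517. Then ICC = 0.517/[s(m − 1)]: about 0.07-0.10 for s = 1 and 0.11-0.16 for s = 0.65.

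**The case against.** **The model may include the group level.** A reader might infer that the planned mixed model treats all patients as independent and that the trial's standard errors are therefore too small. The protocol does not support that. Section 9 lists no random effects, a linear mixed model can carry an IMR-group effect without contradicting any sentence there, and such detail is often left to an SAP, which is not at hand. This stands, and it is why the point rests on section 5.3.

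**The trial may still have enough power.** A reader might also conclude that the trial is underpowered because of clustering. With 111 versus 74 and only starters clustered, power stays at or above the stated 0.80 up to an ICC of 0.10, and the 0.87 reference value is not a protocol figure. This stands as arithmetic. The surplus is not a declared clustering allowance, however: the protocol has already assigned it to treatment drop-out. Whether it suffices for that is a separate question, and the step 3 figures assume no dilution of d.

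**The size is uncertain.** The pilot result concerns fidelity and is not an outcome ICC. Clustering may be weaker than modelled: only 60 of the 78 starters are expected to finish (section 8.2.1), and section 12.2 lets patients who refuse randomisation take IMR, so groups may contain fewer trial patients than the division suggests. At an ICC of 0.01 the effect is negligible. All of this stands.

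**Could 74 hide an allowance?** Three measures taken literally give 66 per arm, so one could read the difference as a margin. Nothing in the listed inputs says so. Even with the factor 0.667, power at 74 + 74 is 0.78-0.82 at ICC 0.05 and 0.72-0.79 at ICC 0.10.

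**The group counts are clerical.** They do not enter the section 5.3 calculation, and 10 versus 14 groups might be compatible if some groups mainly serve non-trial patients. The text does not say this, and 78 versus 85 remains a plain mismatch.

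**Conclusion.** The point holds for the sample size. Section 5.3 states 80% power for 74 per arm on an independence assumption that the protocol's own group delivery calls into question. The direction is certain for any ICC above zero. The size is not, because the ICC is assumed: at the base 74 + 74 the loss runs from about 1 percentage point (ICC 0.01) to about 13 (ICC 0.10, groups of 8.5, all IMR patients clustered). At the planned 111 versus 74, power reaches the target or just exceeds it under the starters-only assumption, so this does not undermine the trial.

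For the analysis the conclusion is conditional. If IMR group were left out of the model, the type I error would be about 0.051-0.073 with starters only clustered, negligible at the low end. Section 9 neither includes nor excludes the group level. The conflicting counts of starters and groups are a confirmed inconsistency that leaves group size undefined. This is a change worth making, but not a fatal flaw.

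**What to change.** - **Section 5.3:** state that IMR is delivered in groups, give an assumed ICC range (for example 0.01 to 0.10) and a group size, and restate power for 111 versus 74 over that range. No additional patients are needed.
- **Section 9:** add a random intercept for IMR group in the IMR arm, with control patients and IMR patients who never start a group as clusters of one, and use small-sample degrees of freedom (Kenward-Roger or Satterthwaite) because there are only 10 to 14 groups. Any clustering by the six outpatient teams can be settled in the SAP.
- **Data collection:** record the IMR group identifier for every patient who joins one. Without it the clustering cannot be modelled afterwards.
- **Sections 8.2.1, 10 and 11:** reconcile 78 versus 85 group starters and 10 versus 14 groups, and say whether non-trial patients share the groups.

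The cost is wording and one data field. The downside is slightly wider intervals and a slightly lower stated power; if the ICC proves close to zero, little is lost.

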8.1.3. Exploratory analysis

The pilot study showed that women significantly more often are IMR completers and that completers at baseline scored better on the IMR-scales and on the GAF (psychosocial functioning). This makes it interesting to examine whether women benefit more from IMR than men and whether patients who at baseline score higher in terms of illness management, psychosocial functioning and symptoms, improve more than patients who at baseline score lower on these domains. Earlier IMR research was often focused on patients with psychotic disorders. We want to investigate whether the effect varies by diagnosis group. We are able to explore this because in the IMR-training of Bavo Europoort chronic patients with various diagnoses participate. Since half of the population of outpatients of Bavo Europoort has an immigrant background, we would like to explore whether IMR for participants from ethnic minorities is as effective as for participants of native background.

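### Whether IMR works better for some patients is to be tested with t-tests and one-way ANOVA, which cannot contain a treatment-by-characteristic term

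*Protocol*

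**What the plan says.** Section 8.1.3 poses four questions about differential benefit, under the heading "8.1.3. Exploratory analysis":

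- Sex: "whether women benefit more from IMR than men".
- Baseline level: whether patients who start with better illness management, functioning and symptoms "improve more than patients who at baseline score lower on these domains".
- Diagnosis: "We want to investigate whether the effect varies by diagnosis group".
- Ethnicity: "whether IMR for participants from ethnic minorities is as effective as for participants of native background".

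Section 9 (Statistics) assigns methods to these questions, presenting them as prediction of the effect on the primary outcome. For "patient characteristics (gender, etnicity, diagnosis) we use t-tests and one way ANOVA". For baseline functioning ("scores on IMR-scales, GAF-scores, Social Functioning Scale and BSI) we use linear regression analysis").

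The only interaction named in section 9 is time by group, for the main comparison. The section names no group x characteristic term. It does not say whether the prediction analyses use the IMR arm, both arms pooled, or both arms compared, and it does not say whether their outcome is the final score or the change.

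**The concern.** The effect of IMR is a difference between randomised arms. Asking whether it is larger in women, in one diagnostic group or in native-born patients asks whether that difference varies, which is a group x characteristic interaction. A t-test or one-way ANOVA on the characteristic compares kinds of patients instead. If women improve more than men under any care, the test is significant and reads as if women gain more from IMR.

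Section 1.2.2 says the research can point to the types of patients for whom IMR could be effective. A prognostic difference reported as differential benefit by sex, ethnicity or diagnosis could influence who is offered the training. The trial randomises a CAU arm and stratifies on psychotic disorder (section 4), so the data for the right test will already be collected.

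**Working it through.** **Inputs.** From section 5.3: effect size 0.40, correlation between measures 0.50, alpha 0.05, power 0.80, 74 per arm before the 3:2 allocation, then 111 and 74. Section 8.2.1 expects the same 111 and 74 at follow-up. Assumed here: two-sided testing, a 50:50 characteristic (the protocol supports this only for ethnicity, where half of the outpatients have an immigrant background), and prognostic effects of 0.2 to 0.5 SD, which are not in the protocol.

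**1. The plan's own figure.** n per arm = 2(1.96 + 0.84)² / 0.40² x (1 + 0.5)/2 = 98.1 x 0.75 = 73.6, so 74 per arm and 148 in total, as stated. The variance scale used below is therefore consistent with the plan's.

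**2. What the one-factor tests estimate.** Write the outcome as a + δT + γS + θTS + error, where T is IMR, S the characteristic, γ its prognostic effect and θ the effect modification in question.

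- t-test within the IMR arm: estimates γ + θ.
- t-test on both arms pooled (IMR share 111/185 = 0.60): estimates γ + 0.60θ.
- group x characteristic term: estimates θ.

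On either reading of the analysis set, γ is mixed in. More patients would not remove it.

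**3. False findings when θ = 0.** Simulation of 4,000 trials per setting, with 111 vs 74 patients, IMR effect 0.40 SD in both subgroups and residual variance 0.75. Share of trials with p < 0.05:

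| Prognostic effect γ (SD) | t-test, IMR arm | t-test, pooled | Interaction test |
|---|---|---|---|
| 0.2 | 23% | 34% | 5% |
| 0.3 | 43% | 62% | 5% |
| 0.4 | 66% | 85% | 5% |
| 0.5 | 85% | 97% | 5% |

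Hand check for γ = 0.3 within the IMR arm: SE = sqrt(0.75 x 2/55.5) = 0.164; 0.3/0.164 = 1.83; Φ(1.83 - 1.96) = 0.45, in line with 43%.

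**4. Baseline score of the same scale.** This holds only if the regression is run as change on baseline, within the IMR arm, with equal variances. Then corr(change, baseline) = (ρ - 1)/sqrt(2(1 - ρ)), and t = r sqrt(109)/sqrt(1 - r²) for n = 111.

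- ρ = 0.5 (plan): r = -0.50, t = -6.03.
- ρ = 0.8 (assumed): r = -0.316, t = -3.48.

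Both arise with an inert IMR. With the final score as outcome and ρ = 0.5, r = +0.50 and t = +6.03, so the sign depends on an outcome that section 9 does not define. In simulation at ρ = 0.5 without moderation, the within-arm change regression was significant in every run, and the group x baseline term in 4.6%.

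**5. Precision of the right test.** For a 50:50 factor, SE = sqrt(v x (2/55.5 + 2/37)), and the detectable difference at 80% power is 2.80 x SE.

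- Mean of two follow-ups, adjusted for baseline: v = 0.75 - 0.25 = 0.50, SE = 0.21, detectable 0.59 SD.
- Single follow-up, adjusted for baseline: v = 1 - 0.25 = 0.75, SE = 0.26, detectable 0.73 SD.

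With v = 0.75, power for an interaction as large as the assumed main effect (0.40 SD) is 0.34.

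**The case against.** The strongest reply is that these analyses are exploratory by the section's own heading, that section 1.2.2 claims only that the research can point to types of patients, and that no confirmatory conclusion depends on them. Power of 0.34 for an interaction of 0.40 SD also means that the trial could not answer these questions well by any method. This stands, and it limits the severity. It does not rescue the tests, because an exploratory analysis still has to estimate the quantity it is meant to explore.

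Three stronger readings are tempting, but the protocol does not support them.

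- A reader might infer that section 9 fixes a simple regression on baseline. It says linear regression, which can carry group and group x baseline terms. Naming those terms is often left to a SAP. For baseline functioning, the point is only that the model and analysis set are left open in a place where one natural choice misleads. No such latitude exists for a t-test or one-way ANOVA.
- A reader might infer that the CAU arm is left out. Section 9 does not say so. The one-factor tests fail on either reading.
- A reader might take t = -6.0 as the size of the whole problem. It belongs to one possible regression for one kind of predictor. GAF, the Social Functioning Scale and the BSI are different instruments, and the formula does not carry over to them. The artefact in change scores also runs against the protocol's own conjecture, which is that higher scorers improve more, so it would not falsely confirm that conjecture.

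**Conclusion.** The point holds for sex, ethnicity and diagnosis: section 8.1.3 asks about effect modification, and section 9 fixes tests that cannot address it. With no true modification, the false-finding rate is 23% to 85% within the IMR arm and 34% to 97% pooled. These figures rest on assumed prognostic effects of 0.2 to 0.5 SD, a 50:50 split and 111 vs 74 patients. The structural failure depends on none of these figures.

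For baseline functioning, the weaker statement holds. Section 9 states no group x baseline term and no analysis set, and a within-arm regression of change on baseline of the same scale would produce r = -0.50 from regression to the mean alone at the plan's correlation.

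This should be fixed, but it is not critical. The primary comparison of IMR with CAU, the primary outcome and the sample size are untouched.

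**What to change.** In section 9, for the section 8.1.3 questions:

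- Replace the t-test and ANOVA sentence with group x characteristic terms (or group x time x characteristic) in the linear mixed model already planned, using both arms.
- State that the regression for baseline scores uses both arms and includes group, baseline score and group x baseline score, with the score kept continuous.
- Report each interaction estimate with its 95% confidence interval, labelled exploratory.

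The cost is a few sentences and model terms, with no new patients or measurements. The downside is wide intervals: for a 50:50 factor with 111 vs 74 patients, correlation 0.5 and baseline adjustment, the smallest interaction detectable at 80% power is about 0.6 SD for the mean of two follow-ups and 0.73 SD for a single one. A 30:70 factor raises the single-follow-up figure to about 0.80 SD. The report should say that a non-significant interaction does not show equal benefit.
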